13.5.2 Reporting Deaths

Regardless of relationship to the exercise intervention, all deaths on study should be reported through and including 28 days after the end of the Off-Study visit. Deaths occurring after this period do not have to be reported as SAEs unless considered related to the exercise intervention. For all SAEs, the Investigator is obligated to pursue and provide information to the SCC in accordance with the timeframes for reporting specified above. In addition, an Investigator may be requested to obtain specific additional follow-up information in an expedited fashion. This information may be more detailed than that captured on the AE CRF. In general, this will include a description of the adverse event in sufficient detail to allow for a complete medical assessment of the case and independent determination of possible causality. Information on other possible causes of the event, such as concomitant medications and illnesses must be provided. In the case of a patient death, a summary of available autopsy findings must be submitted as soon as possible to the Study Coordination Centre.

13.5.3 Non-Serious AE Reporting

Non-serious adverse events should be recorded on the AE CRF (SOM: [Appendix 12](#)) from the time of informed consent until 28 days after cycle 24. All events should be followed to their resolution, until the Investigator assesses them as stable, irreversible, or until the patient is lost to follow-up, whichever comes first.

13.6 AE Monitoring

The Data Safety and Monitoring Committee will convene on a quarterly basis, and additionally at the discretion of the Steering Committee, throughout the study period to review safety procedures, protocols, and specific cases.

13.7 Statistical Analysis of Adverse Events

Adverse event rates will be summarised with frequency and percentage within each arm and across arms. Rates between groups will be compared using the intention-to-treat approach. In addition, AE incidence rates will be summarised by severity and relationship to the intervention. Intervention-related AEs are those judged by the Investigator to be at least possibly related to the intervention. Adverse events with missing severity or relationship to the intervention will be classified as severe and treatment-related, respectively. Patients with multiple occurrences of events will only be counted once at the maximum severity for each preferred term, SOC, and overall. Deaths that occur within 28 days after the 24th cycle clinic visit are defined as on-study deaths.

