Adverse events ¹⁴	X ³		X	X	X	X	X	X	X	X	X	X	X	X	X	X	X	X	X	X	X	X	X	X	X	X	X	
Concomitant medications ¹⁵	X ³		X	X	X	X	X	X	X	X	X	X	X	X	X	X	X	X	X	X	X	X	X	X	X	X	X	

Table 1 Summary of Assessments (Continued)	Screening	On-Treatment Study Period ¹																								Off-Treatment	
		Cycle 0: Baseline ²	Supervised Exercise								Transition			Self-managed exercise program													
		0	1	2	3	4	5	6	7	8	9	10	11	12	13	14	15	16	17	18	19	20	21	22	23	24	
Metabolic Research Studies																											
Research blood (fasting)		X ¹⁶					X ¹⁷						X ¹⁷														X ¹⁷
FFPE tumour specimens		Request ¹⁸																									
Urine specimens		X					X						X														X
Patient Report Outcomes																											
Appx 5 Demographics & Health History Questionnaire		X ¹⁹																									
Appx 8 Exercise Screening Questionnaire		X																									X ²¹
FACT-G, EPIC-26, FACIT-Fatigue, EORTC QLQ-C30, STAI, CES-D, PSQI, falls ²⁰		X ¹⁹			X			X			X			X			X			X				X			X ²¹
BPI-SF and EQ5D ²⁰		X ¹⁹						X						X					X							X	X ²¹
Exercise questions modified from baseline, Modified Godin exercise scale, memory, exercise motivation ²⁰		X ¹⁹						X						X					X							X	
Diet ²⁰		X ¹⁹												X												X	
Cost of Participation								X						X													

TABLE ABBREVIATIONS:

EMR: electronic medical record; CPET: Cardiopulmonary Exercise Test; ECG: Electrocardiogram; SOC: Standard of Care; ECOG: Eastern Cooperative Oncology Group; PSA: Prostate Specific Antigen; EG: Exercise Group; FFPE: formalin-fixed paraffin-embedded; PFS: Progression-free survival; OS: overall survival; SSE: symptomatic skeletal-related events; BPI-SF: Brief-Pain Inventory Short Form; FACT-G: Functional Assessment of Cancer Therapy-General; FACIT: Functional Assessment of Chronic Illness Therapy; EPIC-26: Expanded Prostate Cancer Index Composite Instrument, EQ5D: Euro-Quality of Life 5-dimension; STAI: State-Trait Anxiety Inventory; CES-D: Centre for Epidemiologic Studies Depression

FOOTNOTES:

¹ The study period is comprised of cycles. Each cycle equals 28 days.

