12.2 Power and Sample Size for Primary Endpoint

This is a 1:1 randomised controlled trial in men with MCRPC. Registered and eligible participants will be

randomised with equal probability to one of two intervention regimens: supervised exercise for 12 cycles tapering to self-management for 12 cycles with psychosocial support or psychosocial support alone. We will stratify by whether the men are on active therapy or not at the time of registration (yes/no) and study site. A total of 866 men will enrol in this study to ensure at least 412 men evaluable for OS in each arm.

Null hypothesis (H_0)= There is no difference in OS between patients randomised to the exercise intervention plus psychosocial support vs psychosocial support alone.

Alternate hypothesis (H_A) = There is a difference in OS between patients randomised to the exercise intervention plus psychosocial support vs psychosocial support alone.

Considering a total enrolment period of 36-months and minimum 36 months follow-up for each patient after enrolment; assuming survival time follows an exponential distribution; and assuming a median OS survival of 33.5 months in the control arm, the sample size required to detect a hazard ratio (HR) of 0.78 with 80% power at significance level of 0.05 is 824, 412 men in each arm. Accounting for up to 5% of patients with missing data on OS, we aim to enrol 866 men. If we consider non-compliance of 10% in the intervention arm, which equates to 371 patients in the intervention arm who are compliant, this provides 77.7% power to detect an HR of 0.78, when comparing the 371 compliant patients with the 412 patients in the control arm at the significance level of 0.05.

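### Section 13.7 compares adverse events only as once-per-man percentages over about 23 months, which understates the relative size of any excess in common non-fatal events and makes no allowance for time at risk

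*Combined protocol and SAP*

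**What the plan says.** Section 13.7 sets out the adverse event analysis in one paragraph. The summary is by number and percentage: "Adverse event rates will be summarised with frequency and percentage within each arm and across arms". Repeat events are collapsed: "Patients with multiple occurrences of events will only be counted once at the maximum severity for each preferred term, SOC, and overall". The comparison is one sentence: "Rates between groups will be compared using the intention-to-treat approach". No test, effect measure or denominator is given. The section also promises that "AE incidence rates will be summarised by severity and relationship to the intervention", but it does not define an incidence rate or mention person-time.

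Other relevant places:
- Table 1, footnote 14: events are collected from consent until 28 days after Day 1 of Cycle 24. They are assessed monthly in all men and also at on-site exercise visits.
- Section 13.0: the timing of each event is recorded on the case report form.
- Section 13.2: the expected events are bone pain, pathological fracture, sprain or strain, joint pain, falls and muscle soreness. No frequencies are given.
- Sections 13.1.1 and 13.1.2: fatal disease progression inside the window is reported, with the event leading to death as a Grade 5 SAE.
- Section 12.6: symptomatic skeletal events have Kaplan-Meier, log-rank and Cox analyses.

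**The concern.** The natural reading of Section 13.7 is a comparison of the percentage of men with at least one event. That measure has two weaknesses here.

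First, most of the events listed in Section 13.2 can recur, and the window is long. Once a large share of controls have had at least one episode, the percentage cannot rise in proportion to the underlying hazard, so the ratio between arms shrinks.

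Second, the plan assumes a survival difference, so men in the two arms would spend different lengths of time at risk. Equal hazards would then give unequal percentages.

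At stake is how accurately the trial reports the harm of intense exercise for soreness, sprains, joint pain and falls, which have no time-based comparison elsewhere in the plan. Section 5.4 describes the number of falls as of interest, but Section 12 gives no analysis of that count.

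**Working it through.** **1. Survival assumptions.** Section 12.2 is the source: "assuming a median OS survival of 33.5 months in the control arm", exponential survival, and a sample size to "detect a hazard ratio (HR) of 0.78 with 80% power at significance level of 0.05 is 824, 412 men in each arm". With "Considering a total enrolment period of 36-months and minimum 36 months follow-up for each patient after enrolment" and uniform accrual, the probability of death is 0.665 (control) and 0.576 (exercise), mean 0.6205. The Schoenfeld formula needs 509 events, so N = 509/0.6205 = 820. The Freedman formula needs 514, so N = 828. The stated 824 lies between them, so the assumptions have been read as the plan used them.

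**2. Window.** "Each cycle equals 28 days", so from Day 1 of Cycle 0 the window is 24 × 28 + 28 = 700 days. T = 700/30.44 = 23.0 months.

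**3. Time at risk.** Death hazards are m_c = ln 2/33.5 = 0.0207 per month and m_e = 0.78 × m_c = 0.0161.
- Deaths in the window, 1 − exp(−mT): 37.9% control, 31.0% exercise. With 866/2 = 433 men per arm, that is about 164 and 134.
- Mean months at risk, (1 − exp(−mT))/m: 18.3 and 19.2, a ratio of 1.05.

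**4. Percentage of men with at least one non-fatal event.** With a constant event hazard h and exposure ended only by death:

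P = h/(h + m) × (1 − exp(−(h + m)T))

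The documents give no value for h, so a range is assumed. The exercise arm has HR 0.78 for death throughout.

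| h per month | Control % | Exercise %, equal h | Difference, points | Exercise %, h doubled | Ratio if doubled |
|---|---|---|---|---|---|
| 0.005 | 8.7 | 9.1 | 0.4 | 17.3 | 1.99 |
| 0.01 | 16.5 | 17.3 | 0.8 | 31.2 | 1.89 |
| 0.02 | 29.9 | 31.2 | 1.4 | 51.7 | 1.73 |
| 0.03 | 40.7 | 42.5 | 1.8 | 65.1 | 1.60 |
| 0.05 | 56.8 | 59.1 | 2.3 | 80.1 | 1.41 |
| 0.07 | 67.6 | 70.1 | 2.5 | 87.2 | 1.29 |

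With no survival difference, a doubling shows as 1.88 at a control percentage of 10%, 1.66 at 30%, 1.44 at 50% and 1.14 at 80%. With gamma frailty of variance 1 for variation between men, these become 1.80, 1.50, 1.30 and 1.10.

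**5. First events per person-month.** Mean time to first event, death or end of window is (1 − exp(−(h + m)T))/(h + m). Dividing P by it leaves h. At h = 0.05, control gives 0.568/11.36 = 0.050 and a doubled exercise arm gives 0.801/8.01 = 0.100. The rate ratio is 2.00 for a doubling and 1.00 for equal hazards, whatever the survival difference.

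**6. Totals that include deaths.** The percentage with any SAE including fatal ones is 1 − exp(−(h + m)T). At an equal non-fatal SAE hazard of 0.01 per month it is 50.6% control and 45.2% exercise.

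**7. Detection.** With 433 per arm and HR 0.78, a doubling has power above 99% for control percentages of 20% to 80% (at least 95% with frailty). With equal hazards, a 5% test of percentages rejects 7% to 11% of the time for control percentages of 30% to 60%.

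**The case against.** Once-per-man counting at maximum severity is a coherent summary. The survival effect is small: 5% more exposure, and at most about 2.5 points. Section 13.7 never names the ratio of percentages as its measure; at h = 0.07 the table shows 67.6% against 87.2%, a gap of about 20 points that no reader would miss. The frequencies are assumed, and a hazard doubled evenly to month 23 does not match 48 weeks of supervised training followed by self-management. All of this stands, and it limits the point to one of reporting precision.

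Four stronger readings are tempting, and the documents do not support them:

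- **A survival benefit makes the exercise arm look worse for every event.** This holds only for individual non-fatal terms. Fatal progression is reported as an event, so totals that include deaths fall in the exercise arm (step 6).
- **Section 13.7 is the only between-arm comparison of harm.** Section 12.6 analyses symptomatic skeletal events, including symptomatic fracture and spinal cord compression, by time-to-event methods, and Section 12.7 compares pain.
- **A safety signal would be hidden.** Step 7 shows that a doubling of a common event would be detected; only its relative size is compressed.
- **Competing-risk cumulative incidence, or a count of all episodes, would solve the problem.** When men are followed to death or the end of the window, cumulative incidence equals the crude percentage, so it leaves the survival effect in place. Episode counts are exposed to unequal detection: exercise men are also asked about events at each supervised session (88 planned, Section 6.1).

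**Conclusion.** The point holds as a cheap improvement. Section 13.7 makes no allowance for time at risk or repeat events and does not define its rates. For non-fatal terms affecting about 40% or more of controls, a true doubling would appear as about 1.6 or less. At about 10% or below the distortion is slight, with a ratio near 1.9 to 2.0 (1.80 at 10% with frailty). The assumed survival benefit adds at most about 2.5 points to an individual non-fatal percentage at equal hazards.

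These sizes rest on constant hazards, the Section 12.2 survival assumptions, exposure ended only by death, and event frequencies that the documents do not give. Unequal withdrawal could change the imbalance and cannot be sized from the documents.

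**What to change.** In Section 13.7:

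1. Keep the once-per-man percentages, and state their denominator and the effect measure.
2. For the expected exercise-related terms in Section 13.2, add a between-arm comparison of first events per person-month at risk, or a cause-specific hazard ratio.
3. Report fatal and non-fatal events separately.
4. Use cumulative incidence only where withdrawal has to be handled.
5. Make any total-episode rate secondary, and restrict it to events captured at the monthly contact common to both arms.

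The cost is wording and one or two extra tables; event timing is already recorded. The person-month rate assumes a roughly constant hazard, so it is best split into the supervised and self-managed periods.

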13.1 Definitions

13.1.1 Clinical Adverse Events (AE)

A clinical adverse event is any unfavourable or unintended sign, symptom, or disease temporally associated with the study intervention and occurring in a patient assigned to the intervention. All AEs reported from the date of informed consent until 28 days after the Off-Study visit will be considered. AEs are assessed by the exercise physiologist, trainer, etc. at on-site exercise visits and in all subjects (in person or by phone) on a monthly basis. This includes adverse clinical or laboratory findings, illness, or an exacerbation or progression of a disease/condition present at baseline. A list of standard questions will be used to assess any AEs, provided in the SOM.

In this trial, the study intervention is defined as supervised aerobic and resistance exercise. All potential participants will be screened via their medical charts as well as through in-person assessments to assess cardiovascular contraindications to exercise. Our multi-gated comprehensive approach should systematically identify and screen out any individual for whom this study is contraindicated.

However, rare but serious AEs are possible. Those that may occur during either cardiopulmonary exercise testing (CPET) or exercise training include myocardial infarction (heart attack), stroke, unconsciousness or other serious injury.

- Events during a CPET are rare (<1/100,000 in well individuals and 1/10,000 in sick individuals). A trained health professional (e.g. medical staff and exercise physiologist) will monitor the exercise test in a location staffed by physicians, in the rare event that such an event occurs.
- Similar to a CPET, exercise training may cause temporary risks of an adverse cardiovascular event, such as a heart attack. The CPET with ECG-monitoring that must be completed prior to randomisation will ensure that all randomised participants are healthy enough to engage in exercise training.

Absolute and relative indications for stopping exercise (both testing and training) are provided in [Table 5](#). In the event of a participant presenting with any of the below symptoms exercise should be stopped.

Table 5. Indicators for Stopping Exercise

Absolute indications for Stopping Exercise:

- Suspicion of a myocardial infarction or acute myocardial infarction (heart attack)
- Onset of moderate-to-severe angina (chest pain)

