13.3 Attribution

A suspected adverse reaction means any adverse event for which there is reasonable possibility that the intervention caused the adverse event. For the purposes of safety reporting, “reasonable possibility” means there is evidence to suggest a causal relationship between the intervention and the adverse event.

The Investigator will assign attribution of the possible association of the event with the study intervention using the following definitions:

Unrelated to the exercise intervention: The adverse event is *Unlikely* or *Not Related* to the exercise intervention

Related to exercise intervention: The adverse event is *Possibly*, *Probably*, or *Definitely* related to the exercise intervention.

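### Section 13.7 counts adverse events with a missing relationship as treatment-related in every arm, including the control arm, which is not given the supervised exercise being assessed

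*Combined protocol and SAP*

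**What the plan says.** Section 13.7 sets the rule for incomplete adverse event (AE) records: "Adverse events with missing severity or relationship to the intervention will be classified as severe and treatment-related, respectively". Nothing in the section restricts it to the supervised-exercise arm. The same paragraph gives the tables it feeds: "Adverse event rates will be summarised with frequency and percentage within each arm and across arms", and, as an addition, "AE incidence rates will be summarised by severity and relationship to the intervention". It also states that "Intervention-related AEs are those judged by the Investigator to be at least possibly related to the intervention". The comparison between groups is given separately: "Rates between groups will be compared using the intention-to-treat approach".

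Section 13.1.1 fixes what the relationship refers to: "In this trial, the study intervention is defined as supervised aerobic and resistance exercise". Section 12.2 gives the control arm psychosocial support alone. AEs are nevertheless collected in both arms: Section 13.1.1 has them assessed "in all subjects (in person or by phone) on a monthly basis", and footnote 14 of Table 1 agrees. Section 13.0 lists relationship to the exercise intervention among the details recorded for AEs, again without an arm limit. Section 13.3 offers two categories, related and unrelated to the exercise intervention, and has no not-applicable category.

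**The concern.** Treating an unknown relationship as related is a familiar conservative convention. It guards against understating the harm of the treatment under test, and it makes sense where every arm receives a study product or where the assessor does not know the arm. Neither applies here. Only Arm A receives supervised exercise, and Section 4.6 says that investigators and staff cannot be blinded. For a control man, relatedness to supervised exercise is settled by the design, so there is nothing to impute.

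Applied to Arm B, the rule produces events labelled as caused by a programme the man was not given. It also sits awkwardly with the sentence before it in 13.7, which defines related events by the investigator's judgement; an imputed value is not a judgement. At stake is the credibility of the related-event table in a trial of high-intensity exercise in men with metastatic disease. Sections 13.1.1, 13.2 and 16.2 themselves name cardiovascular and skeletal risks.

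**Working it through.** The plan states no figure on this point, so there is nothing to reproduce. The check has a textual part and an illustrative part.

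**Does the rule reach Arm B?**

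1. 13.7 states the rule with no arm limit. It takes the terms treatment-related and intervention-related to mean the same thing, as I do.
2. 13.7 summarises AEs in each arm and across arms, so control events are in the tables.
3. 13.0 and 13.1.1 collect AEs, with relationship, in all subjects.
4. No section sets relationship for control men to unrelated or not applicable.
5. The AE definition in 13.1.1 does refer to a patient assigned to the intervention. Read literally, that would remove control AEs altogether. This conflicts with points 2 and 3, so it does not take Arm B out of the rule.

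The words *both arms* do not appear in 13.7. Its reach to Arm B is inferred from the absence of a limit together with points 2 and 3.

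**How many control men?**

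Inputs: 866 men (Section 12.2) and 1:1 allocation (Section 4.4), so 866 / 2 = 433 per arm. The share m of control men with at least one AE whose relationship is blank is assumed. Control men wrongly listed = 433 × m.

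| Assumed m | Control men listed as related |
|---|---|
| 1% | 4.3 |
| 2% | 8.7 |
| 5% | 21.7 |
| 10% | 43.3 |

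If the rule covered Arm A only, each entry would be 0.

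**What happens to the excess in Arm A?**

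Let p be the true share of Arm A men with an exercise-related AE (0 in Arm B by definition), and mA and mB the shares with a blank. If blanks occur independently of true related events:

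- reported in Arm A = p + (1 − p) × mA
- reported in Arm B = mB

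All values of p, mA and mB below are assumptions.

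| p | mA | mB | Arm A | Arm B | Difference (points) | True difference (points) |
|---|---|---|---|---|---|---|
| 20% | 5% | 5% | 24.0% | 5.0% | 19.0 | 20 |
| 10% | 5% | 5% | 14.5% | 5.0% | 9.5 | 10 |
| 10% | 2% | 10% | 11.8% | 10.0% | 1.8 | 10 |
| 10% | 5% | 20% | 14.5% | 20.0% | −5.5 | 10 |

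First row: 0.20 + 0.80 × 0.05 = 0.24. With equal blanks the difference moves by 1 point or less. A large loss, or a reversal, needs more blanks in Arm B.

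**Effect on the combined count**, second row, equal arms: as written (14.5 + 5.0) / 2 = 9.75%; with the rule in Arm A only (14.5 + 0) / 2 = 7.25%; truth (10 + 0) / 2 = 5%.

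**The case against.** The case for leaving 13.7 alone has several parts.

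- **The stated comparison is not affected.** The between-group sentence in 13.7 concerns AE rates with no relationship filter, and the breakdown by relationship is an added summary. No test of related events between arms is specified. This stands.
- **Blanks may be rare.** Section 13.3 gives an unrelated category that a site can use for any control event. Section 13.0 calls for relationship to be recorded, 13.5 has the site PI review all AEs, 15.1 makes the site PI responsible for completeness, and 15.4 provides validation checks. This stands: it limits the size but does not make the rule right when a blank does occur.
- **Arm B is not free of exercise.** It is the self-directed exercise group, and Section 5.2 gives it the same cardiopulmonary, walk and strength tests. Some control events could relate to those. But 13.1.1 defines the intervention as supervised exercise, so such events need their own field.
- **Imputing in one arm only is differential handling.** With p = 20% and 5% blanks, the table would read 24% against 0% when the truth is 20% against 0%. This is a fair cost: the imputed Arm A figure is an upper bound and must be shown as one.

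A reader might go further and infer that the rule masks exercise-related harm by shrinking the excess in Arm A. The documents do not support that. They give no blank rate in either arm and no evidence that the field is left blank more often for control men, and with equal blanks the difference barely moves.

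**Conclusion.** The point holds in a limited form. As written, 13.7 turns any blank relationship in Arm B into an intervention-related event in a man not given the intervention, so the Arm B and combined related counts can only be too high. The scale is about 4 to 43 of 433 control men if 1% to 10% have a blank; that range is an assumption. A material change in the difference between arms rests on a second, unsupported assumption of more blanks in Arm B. The missing-severity half of the rule is not at issue, and neither the overall survival analysis nor the unfiltered AE comparison is affected. This is a minor correction to safety reporting.

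**What to change.** Amend 13.7 so that:

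1. The missing-relationship rule applies to the supervised-exercise arm only.
2. In Arm B, relationship to supervised exercise is recorded as not applicable or unrelated. If wanted, relationship to the study exercise tests is captured separately.
3. Related events in Arm A are reported twice: as judged by the investigator, and with blanks imputed as related. The second is labelled an upper bound.

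The between-group comparison of AE rates can stay as it is. At the same time, reconcile the AE definition in 13.1.1 with collection in all subjects.

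The cost is a short edit to 13.7, possibly one more option on the AE form, and one extra table column. An arm-specific rule also needs the arm to be known at that step. Section 4.6 promises a blinded statistician for the prespecified primary and secondary analyses; AEs are not among the endpoints listed in 12.1, so the conflict is small.
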